10.4.2. Safety Analyses

The safety analyses will be based on the Safety Population. All safety analyses will be conducted for all patients and separately for DLB and PDD patient subgroups.

Safety will be assessed by summarizing and analyzing AEs, laboratory analytes, vital signs, ECG parameters, physical examination findings, concomitant medications, MMSE scores, MoCA scores, and C-SSRS scores.

10.4.2.1. Adverse Events

AE verbatim text will be coded and classified by body system and preferred (coded) term using the MedDRA. AEs will be assigned to the treatment based on the last dose taken. All AEs will be listed. AEs, Drug related AEs, SAEs, AEs that lead to discontinuation of investigational product will be summarized by treatment group. AEs will be summarized separately for the Single-Blind Run-In Period and the Double-Blind Treatment Period.

10.4.2.2. Clinical Laboratory Tests

Summaries of clinical laboratory data will be provided for subjects in the Safety Population. No inferential statistics will be provided.

Quantitative values and change from baseline in quantitative values will be summarized by planned nominal time and treatment for each quantitative laboratory value. Listings of all laboratory results and reference ranges will be provided. For multiple laboratory assessments at the same time point, the worst value will be used for the data summaries.

Laboratory values that fall outside of the reference range will be flagged as H=High or L=low.

A laboratory shift table may be provided to show the baseline to the worst post value. Laboratory values that do not meet the laboratory abnormalities will be assigned N=normal in the shift table.

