If a subject discontinues during the placebo run-in period, the Early Termination Visit sleep laboratory assessment will not be required, but all other early termination procedures must be performed. If a subject meets discontinuation criteria during double-blind treatment, an Early Termination Visit (including sleep laboratory) will be required.

Subjects who meet any of the following laboratory abnormality criteria will be discontinued from the study (adapted from FDA Draft 2009 Guidance for Industry Drug-Induced Liver Injury: Premarketing Clinical Evaluation):

- ALT or AST >5xULN, confirmed by immediate repeat testing
- ALT or AST >3xULN and TBL >2xULN or INR >1.5, confirmed by immediate repeat testing
- ALT or AST >3xULN, confirmed by immediate repeat testing, with a concurrent report of fatigue, nausea, vomiting, right upper quadrant pain or tenderness, fever, rash, and/or eosinophilia (>5%). If, upon repeat testing of liver chemistry, the symptoms outlined have resolved, but the liver chemistry still meet the noted criteria, subjects should discontinue study treatment.

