8.3.2.1.2. Adverse Events of Special Interest (AESIs)

Inform the medical monitor if subjects report the following types of AEs: accidents or injuries (eg, falls, fractures), hepatic disorder (eg, increased serum aminotransferase, increased bilirubin), skin reactions (eg, dry skin, rash), or QT prolongation (eg, QT interval prolonged, syncope). The medical monitor may instruct you to collect additional relevant information on these events.

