10.4. Key Elements of Analysis Plan

The primary objective of this study is to evaluate the efficacy of nelotanserin in reducing the nightly frequency of characteristic RBD behaviors (sum of simple/major and complex events per 10 minutes of REM sleep) following 4 weeks of treatment for patients with DLB.

Descriptive statistics for all efficacy and safety measures over the course of the study will be presented for the DLB patient subgroup, as well as for the PDD patient subgroup and the full patient sample. Continuous data will be summarized by means, standard deviations, standard errors, medians, interquartile ranges, maximum observed value, minimum observed value, and number of subjects. Categorical data will be summarized by frequency counts and proportions.

Listings will be sorted by subject and time. Summaries will be presented by treatment, disease type, and time. Version 9.2 or higher of the SAS system will be used to analyze the data as well as to generate tables, figures, and listings. Further details of analyses to be performed will be provided in the statistical analysis plan (SAP).

Analysis datasets will be constructed using version SAS 9.2 or later following current CDISC guidelines.

Missing data will not be imputed for primary analysis. If there are missing data at EOS visits for the primary or key secondary efficacy endpoints, the impact of missing data will be evaluated by testing the primary analysis model using the subset of the Randomized Safety Population who have an evaluable primary endpoint assessment at baseline, with any missing values at EOS imputed using multiple imputation. Details of imputation and any changes or refinements necessary will be documented in the SAP.

Compliance:

- Summary of treatment compliance will be presented by treatment arm. The number and percentage for compliance expressed as a categorical variable (<80%, ≥80% to ≤120%, and >120%) will also be presented by treatment arm.
- For efficacy endpoints derived based on the study diary, if subjects report values for < 50% of days during a weekly period, all daily values for that item (and thus all endpoints that are computed using that item) will be set to missing for that week.
- Efficacy endpoints assessed with ActiGraph will only be calculated for each weekly period during the run-in and double-blind treatment periods for subjects with non-missing data for at least 4 nights during that week.

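### Section 10.4.2.2 plans no per-arm count of subjects crossing the protocol's own liver-test limits, and its only worst-value table is optional and cannot tell a mild rise from one above 5xULN

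*Combined protocol and SAP*

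**What the plan says.** **Laboratory analysis.** Section 10.4.2.2 states: "Quantitative values and change from baseline in quantitative values will be summarized by planned nominal time and treatment for each quantitative laboratory value". Section 10.4 fixes the statistics: "Continuous data will be summarized by means, standard deviations, standard errors, medians, interquartile ranges, maximum observed value, minimum observed value, and number of subjects". Section 10.4.2.2 adds "Listings of all laboratory results and reference ranges will be provided" and "Laboratory values that fall outside of the reference range will be flagged as H=High or L=low". Where several results share a time point, the worst is used. The one display of the worst value over the whole post-baseline period is conditional: "A laboratory shift table may be provided to show the baseline to the worst post value". Its categories are high, low and normal.

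**Limits that drive conduct.**
- Exclusion criterion 18 (Section 6.2.2) bars AST, ALT or TBL above ULN.
- Section 6.5.1 lists discontinuation criteria, the first being "ALT or AST >5xULN, confirmed by immediate repeat testing". Others combine ALT or AST above 3xULN with TBL above 2xULN or INR above 1.5, or with symptoms or eosinophilia.
- Section 8.3.2.5 calls for immediate confirmation and retesting once or twice weekly after an aminotransferase above 3xULN or TBL above 2xULN.
- Section 8.3.2.1.9 defines a Hy's law case and makes it an SAE.

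**Adverse events.** Section 8.3.2.1.2 names four special-interest groups. The hepatic one is given as "hepatic disorder (eg, increased serum aminotransferase, increased bilirubin". Section 10.4.2.1 lists the planned summaries: "AEs, Drug related AEs, SAEs, AEs that lead to discontinuation of investigational product will be summarized by treatment group". The special-interest groups are not among them.

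**The concern.** The protocol acts on multiples of ULN and on combinations of ALT or AST with TBL or INR, but the analysis section reports on neither scale. A mean or median across an arm responds little to one or two large rises. The shift table might not be produced. If it is, it cannot show how high a value went. Because entry requires values at or below ULN, nearly every subject should start as normal, so the table would reduce to a count of subjects who ended above ULN by any amount.

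The stake is how well a hepatic difference between arms can be seen. Section 3.1.2 reports earlier exposure of up to 14 days, while Table 2 gives 28 to 40 days of double-blind treatment. The Day 14 chemistry is confined to liver tests (Table 2, note 16). Stored bile acid samples may be analysed if a liver signal appears (note 15), yet no planned table is built to show such a signal by arm.

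**Working it through.** The plan states no figure on this point, so there is none to reproduce. The check compares the planned outputs with the limits, then illustrates the size.

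**1. What each planned output can show**
- *Statistics at scheduled times:* the maximum reveals a crossing at a scheduled visit. It is one value per arm, visit and analyte, so it does not count subjects. The ALT and TBL maxima may belong to different people, so no joint criterion can be read from them.
- *High/low flags and optional shift table:* 1.1xULN and 5xULN both read as high.
- *Listings:* complete, but by subject and not summarised by arm.
- *AE, SAE and discontinuation tables:* by arm, but by coded term. A mild rise that led to extra monitoring can carry the same term as a rise above 5xULN.
- *Per-arm count above 3xULN, 5xULN, TBL 2xULN, or meeting a joint or Hy's law criterion:* none in the supplied text.

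**2. Sensitivity of the mean.** Inputs: n = 26 per arm (Section 6.1). Assumption: the other 25 subjects stay at b times ULN, with b from 0.3 to 0.8. One subject rises from b to a peak P.
- Change in arm mean = (P − b)/26. Arm mean = (25b + P)/26.
- P = 5: change (5 − 0.8)/26 = 0.16 to (5 − 0.3)/26 = 0.18xULN; arm mean 0.48 to 0.96xULN.
- P = 3: change (3 − 0.8)/26 = 0.08 to (3 − 0.3)/26 = 0.10xULN; arm mean 0.40 to 0.88xULN.

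The full-arm mean stays within normal throughout. In the subgroups it may not. With P = 5 and b = 0.8 it reaches 1.05xULN at 17 per arm (DLB) and 1.27xULN at (52 − 34)/2 = 9 per arm (PDD).

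**3. Unscheduled retests.** Assume ULN 40 U/L and baseline 20 U/L. A subject has 3.1xULN (124 U/L) at a scheduled visit and 6xULN (240 U/L) on the retest.
- Scheduled value only: (124 − 20)/26 = 4.0 U/L on the mean, maximum 124 U/L.
- Retest included: (240 − 20)/26 = 8.5 U/L, maximum 240 U/L.

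The 3xULN crossing is visible either way. Whether 5xULN was passed depends on where the retest goes. Section 10.4.2.2 does not say, since its worst-value rule covers only results at one time point.

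**4. How many crossers to expect.** The chance of at least one in 26 is 1 − (1 − p)^26. For assumed true rates of 1%, 2%, 5% and 10% this is 23%, 41%, 74% and 94%. With 0 of 26, the exact one-sided 95% upper limit is 1 − 0.05^(1/26) = 10.9%. With 1 of 26, the exact two-sided 95% interval is 0.1% to 19.6%. The counts will be small and descriptive.

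**The case against.** The strongest reply is that the crossings are already captured. Section 8.3.2.1.1 treats a laboratory finding that leads to extra monitoring or tests as clinically significant and an AE. Every aminotransferase above 3xULN or TBL above 2xULN triggers such testing. The limits in Section 6.5.1 lead to discontinuation, and Hy's law cases are SAEs. All three kinds of event are summarised by arm. With about 52 subjects, full listings and a DMC reviewing laboratory safety data, a handful of cases could be counted by hand.

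Most of this stands, and it rules out several stronger readings:
- A reader might infer that liver tests are analysed only by mean change. Section 10.4 adds medians, maxima and minima, and Section 10.4.2.2 adds flags and listings.
- A reader might infer that crossings will never be tabulated. Section 10.4 defers further detail to a SAP, and no separate SAP text was among the material reviewed. What can be said is that the supplied text does not plan the table.
- A reader might infer that a peak on a retest leaves no trace. If a scheduled sample triggered the retest, that crossing is already in the scheduled summary. Only a first detection at an unscheduled visit could be absent altogether, and the text does not say that such results are excluded.
- A reader might infer that the protocol ranks liver injury as its main risk. Hepatic disorder is one of four unranked special-interest groups, although liver monitoring is the most intensive.

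The reply does not supply per-arm counts by ULN multiple or the joint criteria, and counting by hand after unblinding is not prespecification. The plan does prespecify a threshold count elsewhere: Section 10.4.2.5 compares by arm the proportion with a UPDRS composite rise of at least 5 points.

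**Conclusion.** The gap is real but limited: it concerns how liver results are presented, not data collection or safety action. The supplied text plans no per-arm count against the protocol's own limits, leaves the only worst-value table optional and too coarse, does not place unscheduled retests, and does not summarise the special-interest groups by arm. The means cannot fill the gap: one subject of 26 at 5xULN shifts the arm mean by 0.16 to 0.18xULN. That figure rests on the assumed 0.3 to 0.8xULN for everyone else, and the U/L example on an assumed ULN of 40 and baseline of 20. The maximum would show a crossing at a scheduled visit but would not count subjects or link ALT to TBL. If a SAP already specifies such a table, only the protocol wording needs aligning.

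**What to change.** In Section 10.4.2.2, replace the optional shift table with a required table by arm, for the Randomized Safety Population and for DLB and PDD separately. It should count subjects whose worst post-baseline value, including unscheduled, repeat and early-termination samples, exceeds limits already in the protocol:
- ALT or AST >ULN, >3xULN and >5xULN;
- TBL >2xULN;
- ALT or AST >3xULN with TBL >2xULN or INR >1.5;
- the Hy's law definition in Section 8.3.2.1.9.

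State whether joint criteria are judged within one sample or on separate peaks. Add a plot of peak ALT against peak TBL by arm. In Section 10.4.2.1, add subject counts by arm for each special-interest group in Section 8.3.2.1.2.

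The cost is a few programmed outputs from data already collected. Sample size, power and alpha are unaffected, and no clinical rule, sample or visit changes.

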10.4.2.3. Vital Signs, Electrocardiograms, Physical Findings, and Other Safety Evaluations

Descriptive summaries of medical history, vital signs, weight, and ECG parameters will be presented separately for each study visit and treatment group. Clinically significant abnormal morphological ECG findings will be summarized by study visit.

Abnormal physical examination findings will be summarized to include the number and percentage of subjects experiencing each treatment-emergent abnormal physical finding.

These data will be summarized by treatment group.

10.4.2.4. Suicidal Ideation and Behavior (C-SSRS)

Descriptive summaries of scores on the C-SSRS will be presented separately for each study visit and treatment group. Scores will consist of 3 composite values: suicidal ideations, suicidal

behaviors, and suicidal ideations or behaviors. Each value will be binary: subjects answering ‘yes’ to one or more of the ideation items (items 1-5) will be classified as having suicidal ideations; subjects answering ‘yes’ to one or more of the behavior items (items 6-10) will be classified as having suicidal ideations; and subjects answering ‘yes’ to one or more of either set of items (items 1-10) will be classified as having suicidal ideations or behaviors.

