8.3.2.6. Assessment of Suicidality

Subjects will be assessed for suicidality before and during the study using the C-SSRS. Subjects considered to be at significant risk will be excluded from the study. The C-SSRS is a brief measure which is designed to assess severity and change of suicidality by integrating both behavior and ideation. It assesses intensity of ideation (a potentially important marker of severity), specifically asking about frequency, duration, controllability, deterrents, and reasons for the ideation which was most severe during the respectively assessed timeframe. Suicidal behavior is also assessed by asking further questions to categorize the behaviors into actual, interrupted, or aborted attempts; as well as preparatory and non-suicidal self-injurious behavior. The C-SSRS will be completed by a rater trained and certified to administer this scale. Any change in C-SSRS score indicating the presence of suicidality should be evaluated by the investigator for clinical significance to determine continued study eligibility ([Section 6.3](#)) and appropriate clinical actions (including but not limited to a referral to a mental health professional).

Clinically meaningful suicidal ideation, suicidal behavior and completed suicide should be recorded as AEs.

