10.4.4. Other Analyses

Additional analyses of the data may be conducted as deemed appropriate and will be detailed in the SAP. Further analyses of the data not specified in the SAP may be undertaken as post hoc analyses after completion of the study. Results of all study assessments will be included in an appendix to the study report.

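### The C-SSRS rule in section 10.4.2.4 labels a yes on the behavior items as ideation, so read literally the ideation and combined composites coincide and the behavior composite has no rule

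*Combined protocol and SAP*

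**What the plan says.** Section 10.4.2.4 of the protocol plans descriptive C-SSRS summaries by visit and treatment group. It names three binary composites, in this order: suicidal ideations, suicidal behaviors, and the two combined. Three rules follow, each for subjects answering yes:

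- Items 1-5: "to one or more of the ideation items (items 1-5) will be classified as having suicidal ideations".
- Items 6-10: "to one or more of the behavior items (items 6-10) will be classified as having suicidal ideations".
- Items 1-10: "to one or more of either set of items (items 1-10) will be classified as having suicidal ideations or behaviors".

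The first and second rules assign the same label. Section 10.4.2 lists C-SSRS scores among the safety analyses and adds: "All safety analyses will be conducted for all patients and separately for DLB and PDD patient subgroups". Section 8.3.2.6 describes the scale as covering both ideation and behavior but gives no scoring rule. Section 10.4 leaves further analysis detail to the SAP. The documents contain no separate C-SSRS derivation.

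**The concern.** A rule that turns item answers into a reported category has to produce the categories it announces. This one announces a behavior composite and never assigns anyone to it, while the ideation composite receives both item sets.

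A programmer who follows the text literally would produce a table with two identical rows (ideation and combined) and no behavior row. A subject reporting a suicidal behavior without ideation would appear as an ideation case. A programmer who corrects the label without comment departs from the written rule and leaves no trace of why. Either way, the distinction that the section's own title draws is not secured by its text. No efficacy test, eligibility rule or subject management depends on these composites.

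**Working it through.** The plan states no figure to reproduce here, so the check is one of logic, followed by a scale for the possible miscount.

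**Inputs.** The three rules come from section 10.4.2.4. Group sizes come from section 6.1 and the protocol summary: about 52 randomized, 26 per arm, of whom about 34 have DLB, 17 per arm. PDD is taken as 52 − 34 = 18, or 9 per arm if split evenly. That even split is an assumption, though randomization is 1:1 and stratified by disease type (section 7.2).

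**Step 1: the rules as logic.** Let I = a yes on any of items 1-5 and B = a yes on any of items 6-10.

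- Intended: ideation = I; behavior = B; combined = I or B.
- As written: ideation = I or B; behavior = no rule; combined = I or B.

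| I | B | Intended (ideation, behavior, combined) | As written |
|---|---|---|---|
| 0 | 0 | 0, 0, 0 | 0, undefined, 0 |
| 0 | 1 | 0, 1, 1 | **1**, undefined, 1 |
| 1 | 0 | 1, 0, 1 | 1, undefined, 1 |
| 1 | 1 | 1, 1, 1 | 1, undefined, 1 |

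Written ideation equals the combined composite in all four rows. It departs from the intended value in one row, behavior without ideation. The behavior composite is undefined in all four. These are counts of logical cases, not frequencies.

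**Step 2: item-level check.** All 2^10 = 1,024 yes/no patterns on items 1-10 were enumerated.

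- As written, ideation and combined differ in 0 patterns, and no pattern is classified as behavior.
- The behavior-only patterns number 1 × (2^5 − 1) = 31. All are counted as ideation.
- With the second rule relabelled, ideation and combined differ in exactly those 31 patterns, and behavior is defined as a yes on any of items 6-10.

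**Step 3: possible size in the table.** Let b be the number of behavior-only subjects in an arm at a visit. The ideation percentage is then too high by 100 × b/n points. The documents give no event rate, so b is an assumption, shown from zero upward.

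| Group (n per arm) | b = 0 | b = 1 | b = 2 |
|---|---|---|---|
| All patients (26) | 0 | 1/26 = 3.8 | 2/26 = 7.7 |
| DLB (17) | 0 | 1/17 = 5.9 | 2/17 = 11.8 |
| PDD (9, assumed) | 0 | 1/9 = 11.1 | 2/9 = 22.2 |

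**Step 4: search for a correction elsewhere.** The other mentions of the C-SSRS are in the protocol summary, section 8.3.2.1.1, section 8.3.2.6, section 10.4.2 and the notes to Table 2. They cover timing, scale version, AE recording and the list of safety analyses. None defines the behavior composite.

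**The case against.** The strongest reply is that this is a slip of one word which the section itself resolves. The three composites and the three rules appear in the same order, the second rule names the behavior items, and the third treats the two item sets as distinct. Read by position, the derivation is there with the wrong label. The literal rule also cannot fill the three-composite table that the section calls for, so a careful programmer would notice.

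The consequences are limited too. Section 8.3.2.6 says: "Clinically meaningful suicidal ideation, suicidal behavior and completed suicide should be recorded as AEs". Section 10.4.2.1 says: "AEs, Drug related AEs, SAEs, AEs that lead to discontinuation of investigational product will be summarized by treatment group". Section 10.4.4 adds: "Results of all study assessments will be included in an appendix to the study report". Exclusion 15 in section 6.2.2 removes subjects endorsing ideation items 4 or 5 at screening or judged to be at significant suicidal risk, and double-blind treatment lasts about four weeks, so few behavior-only cases may arise. The SAP and table programs, which are not available here, may already be right.

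Most of this stands. The intent is clear, the table is descriptive, and b may well be zero. It does not make the operative wording right. The AE route is only a partial substitute, because it depends on a judgment of clinical significance (sections 8.3.2.1.1 and 8.3.2.6), whereas the C-SSRS summary classifies every yes. That summary is also the only planned by-visit, by-arm display of the scale's behavior items.

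**Conclusion.** The concern holds. As written, the ideation composite is identical to the combined composite, and the announced behavior composite has no rule. This follows from the text alone and needs no assumption about event rates.

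The practical size is small and uncertain. The miscount equals the number of behavior-only subjects at a visit: none if there are none, and 3.8 percentage points per such subject with 26 per arm. The subgroup figures rest on the planned 17 per arm for DLB and an assumed 9 per arm for PDD. Whether the error reaches the report depends on the SAP and the programs. The composites can be rebuilt from the item answers at any time, so nothing is lost permanently. The text should still be corrected, because it is the only derivation of a suicidality category in the documents.

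**What to change.** In section 10.4.2.4, in the clause for items 6-10, change the assigned label from *suicidal ideations* to *suicidal behaviors*. Leave the rules for items 1-5 and items 1-10 as they are. Then confirm that the SAP and the table specifications use the same three derivations.

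The cost is a one-word correction and a check of the specifications. It calls for no new data and no change to any study procedure.
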